#### Opioid side effect variables

1. Constipation
  - # of ileus events – search ileus in epic search tool
  - days until first stool – will use first post-operative day which stool documented (i.e. POD#3)
  - total stools, stools/day
  - enema use
2. Nausea
  - # emesis (daily and total per day)
  - # anti-emetic doses (including Zofran, Compazine, granisetron, Benadryl, lorazepam, cyproheptadine, scopolamine; daily and total per day)
3. Itching
  - # days naloxone infusion required

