### 3. Study Endpoints/Events/Outcomes

- 3.1. Primary Endpoint/Event/Outcome: Primary outcome focuses on the total opioid requirement (morphine equivalent per body weight) over the operative and post-operative PICU course (which may range upwards of 7 days in some transplant cohorts). The hypothesis is that magnesium sulfate use will decrease this dosage compared to controls, however measurements will be used to determine whether the intervention does not have any statistical difference as well (or even increases doses, which would be otherwise unexpected in the literature). We intend to pilot 30 prospective transplant patients (liver, TPIAT). Retrospective control data will consist of the last 60 transplants (30 liver, 30 TPIAT), which was determined based on original power analysis targets for a larger-based study anticipated in the future. The study will be stopped prematurely if during obligated data reviews it is determined that opioid needs are increasing. The study will also be halted if 2 patients develop clinically significant adverse reactions secondary to magnesium, at minimum until able to further review dosing and protocols. If arrhythmia (other than transient bradycardia), respiratory failure, or coma are encountered once (also deemed secondary to magnesium), the study will be halted immediately with that patient. Per above, if encountering more frequent anemia than typical post-transplant, the study will be halted to evaluate lab frequency's effect. The study will also be halted for further review if there is a dosing error. A list of data measures is provided in a secondary attachment with this protocol.
- 3.2. Secondary Endpoint(s)/Event(s)/Outcome(s): Secondary outcome data will evaluate total opioid use by post-operative day (i.e. POD#1, POD#2, POD#3, etc) to help determine any variance in effect based on proximity to the surgery as well. Secondary outcomes will also focus on other opioid variables, including amount of 'requested' (PRN) opioids versus what is scheduled. Secondary outcomes will also include opioid side effect data, since these would hypothetically be less if MgSO4 does indeed lessen opioid needs. We will collect 'pain scores' as well, however literature suggests these are often difficult to

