## 12. Withdrawal of Participants

**12.1. Withdrawal Circumstances:** Participants are free to withdraw from participation in the study at any time upon request. An investigator may terminate participation in the study if:

1. Any clinical adverse event (AE), such as secondary toxic reaction to magnesium sulfate, laboratory abnormality, or other medical condition or situation occurs such that continued participation in the study would not be in the best interest of the participant. Specifics regarding secondary reactions:
  - regarding the hemodynamic adverse effects of magnesium: the drug will be halted for etiologic evaluation in the presence of confirmed hypotension or sustained bradycardia; if deemed secondary to magnesium that patient's therapy will be permanently discontinued
  - regarding sedative effects: the PICU team addresses sedation goals each day with rounds and follow up; preference with over-sedation will be to decrease other analgesia/sedative infusions as able given overall goal of this study (i.e. lower opioids, benzodiazepines, dexmedetomidine first as able). If deemed unable to decrease other infusions or already at a minimum, and over-sedation still present, then magnesium infusion will be discontinued.
  - regarding frequency of blood draws: blood draws are already frequent in this population of patients in initial 2 days post-op (typically every 6

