## 13. Risks to Participants

*13.1. Foreseeable Risks:* This would include the potential for known side effects from magnesium toxicity, namely: hypotension, cardiac arrhythmia, hyporeflexia, effects on other electrolytes (such as potassium and calcium), muscle weakness, respiratory depression (secondary to muscle weakness), and increased sedation (including when combined with opioids and benzodiazepines). These toxic risks are cited typically at levels of > 4-4.5 mg/dL. We will minimize this risk by targeting magnesium thresholds below this. Hypotension is monitored for via routine serial blood pressure monitoring in all ICU patients, and can be treated with IV fluid resuscitation as needed (standard for hypermagnesemia treatment). Cardiac arrhythmia is monitored for via cardiac telemetry in all ICU patients, and cardiology specialists and arrhythmia resuscitation techniques are available per standard ICU care. Both of these are risk factors that are present in these populations regardless of magnesium use, however if these conditions are felt potentially contributed to by hypermagnesemia the infusion will be stopped for further evaluation. Electrolyte abnormalities are also common in ICU populations and are monitored routinely per post-transplant protocols. Respiratory depression is monitored routinely in this population as well, however if secondary to perceived muscle weakness out of proportion to standard post-operative course, the magnesium infusion will be stopped as well. Sedation and other analgesia is routine in post-operative transplant care and is addressed and titrated based on daily goals. Decreasing other sedatives will take precedent over magnesium in cases of oversedation given the overall objective of the study. Increased blood draws may occur during monitoring, however in 48 hours of infusion may result in only 4-8 mL of extra blood specifically from magnesium draws alone, which clinically seems insignificant relative to overall course. There is potential for dosing error as is for all PICU delivered medications, however correct units for MgSO4 has been updated in UMMCH pump library, and there is additionally standard ICU regulations per institutional and leadership for routine drip/dose checks. The only other potential foreseeable risk would be that of intravenous line capability. Post-operative transplant patients require multiple IV

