### ***SECONDARY OUTCOMES***

#### opioid variables

1. Morphine Equivalent daily variance (daily dose/kg on each post-op day)
2. Total days on IV opioids
  - will use post-operative day when IV opioid discontinued (i.e. POD#6)
3. Total days on any opioid
4. PCA variables
  - # of demands, # of deliveries (daily and total values)
  - # of escalations in infusion dose
5. Scheduled vs PRN dosing
  - scheduled dosing includes PCA infusion dose and scheduled IV or PO opioids
  - PRN includes PCA delivered doses and PRN opioids delivered

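### The anti-emetic dose count pools seven drugs with no rule on indication or order type, and itching is measured only by naloxone days, so both can move with prescribing rather than symptoms

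*Combined protocol and SAP*

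**What the plan says.** Section 15.1, under the opioid side effect variables, lists two nausea measures. The first is a direct count, "emesis (daily and total per day". The second is a treatment count, "anti-emetic doses (including Zofran, Compazine, granisetron, Benadryl, lorazepam, cyproheptadine, scopolamine; daily and total per day". Under itching there is a single item, the number of "days naloxone infusion required".

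Section 15.1 does separate scheduled from as-needed use for opioids ("PRN includes PCA delivered doses and PRN opioids delivered"). It makes no such split for anti-emetics.

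The reason for collecting these variables is in section 3.2: "Secondary outcomes will also include opioid side effect data, since these would hypothetically be less if MgSO 4 does indeed lessen opioid needs".

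Section 15.3 names emesis counts and naloxone days among the count outcomes. It does not name anti-emetic doses. Its adjusting covariates are transplant type, age and gender. The comparison is with a retrospective chart-review cohort (5.1), and 18.1 says that no blinding is required.

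**The concern.** A dose count measures prescribing. It tracks nausea only if the doses counted were given for nausea and if the habit of ordering them was the same in both cohorts. Nothing in 15.1 secures either condition.

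Lorazepam is a benzodiazepine, and the protocol itself treats benzodiazepines as sedatives (12.1, 13.1). Lorazepam appears nowhere in the data list except under nausea, so a dose given for sedation has no other place to be recorded. Benadryl ordered for itching would be counted as nausea treatment and missed by the itching measure. A change in routine prophylaxis orders between the historical and prospective years would look like a change in nausea.

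What is at stake is the reading of two secondary comparisons. Section 14.1 names itching and nausea among the opioid effects that the trial hopes to lessen. A difference in either measure could be reported as fewer opioid side effects when only ordering had changed.

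**Working it through.** **The plan's own figures.** The documents state no expected count, variance or power for any side-effect outcome. The power table in 15.2 concerns morphine equivalents only. It reproduces: 2 × (1.960 + 0.842)² × 8.3² / 3.49² gives 89 per group, against 90 tabulated. It has no bearing on this point.

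**Whether the design corrects a shift in prescribing.**

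| Safeguard | What the plan has |
|---|---|
| Counting rule by indication | None in 15.1 |
| Scheduled versus PRN split | Opioids only |
| Blinding of those who prescribe | None (18.1) |
| Concurrent controls | None; historical chart review (5.1) |
| Adjustment for calendar time or sedation practice | None in 15.3 |

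**How far the count can move with nausea held fixed.** Let s be the share of counted doses given for reasons other than nausea, and x the relative fall in those doses in one group. Doses given for nausea are the same in both groups. The apparent dose ratio is

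(1 − s) + s(1 − x) = 1 − s·x.

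Both s and x are assumptions, because the documents give neither.

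| s | x = 0.2 | x = 0.5 | x = 0.8 |
|---|---|---|---|
| 0.10 | 0.98 | 0.95 | 0.92 |
| 0.25 | 0.95 | 0.875 | 0.80 |
| 0.50 | 0.90 | 0.75 | 0.60 |

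The formula is symmetric in sign. A rise of one half at s = 0.25 gives 1 + 0.25 × 0.5 = 1.125.

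**How often such a shift would reach significance.** This was a simulation under further assumptions: 60 controls and 30 study patients, a mean of 10 doses, overdispersed counts with coefficient of variation (CV) 0.5, 0.7 or 1.0, and an unadjusted test of the log ratio of means at two-sided 5%. Doses for nausea do not change.

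| Scenario | CV 0.5 | CV 0.7 | CV 1.0 |
|---|---|---|---|
| No shift (s·x = 0) | 5.5% | 5.8% | 6.2% |
| s = 0.25, x = 0.5 | 22.6% | 14.9% | 11.0% |
| s = 0.50, x = 0.5 | 70.2% | 45.0% | 27.1% |

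These figures show that the mechanism is strong enough to matter under plausible inputs. They do not estimate its size in this trial.

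**Itching.** Let k be the share of treated itching that is managed with naloxone infusion. With equal itching in both cohorts and equal duration of treatment, the ratio of recorded days is k(magnesium) / k(control). It equals 1 only if the two shares match, and a patient treated in any other way contributes zero. The documents give no value for k.

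**Emesis.** A direct count of episodes does not depend on why any drug was ordered, so this mechanism does not reach it.

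**The case against.** The strongest reply is that nausea does not rest on the dose count. Emesis is listed first in 15.1 and is the nausea measure that 15.3 names for modelling. That stands, and it confines the point to one of two measures.

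It can also be said that the phrase in 15.1 means doses given as anti-emetics, so that sedative or antipruritic doses were never meant to count. This is a fair reading, but no rule tells an abstractor to apply it. Section 19.2 admits that some data elements need subjective chart searching. The ambiguity remains.

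The documents do not say that Benadryl was given for itching here, that anti-emetics were ordered as prophylaxis, or that orders changed over time. Those are assumptions from general practice. Likewise, naloxone days are counted in the same way in both cohorts, and a narrow measure is not biased merely because it is narrow. Both remarks stand. They limit the claim to what can happen.

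A reader might infer more: that the over-sedation rule in 12.1 ("lower opioids, benzodiazepines, dexmedetomidine first as able") withdraws lorazepam from magnesium patients and so biases the count in favour of magnesium. The documents do not support that. The sentence around those words concerns infusions, and the only benzodiazepine that the data list records as an infusion is midazolam. Section 13.1 is looser ("Decreasing other sedatives will take precedent over magnesium in cases of oversedation given the overall objective of the study"), so some spill-over to lorazepam doses is possible. But controls had no study infusion to reduce, so lowering other sedatives was the course open to them as well. No net direction follows.

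**Conclusion.** The concern holds in a limited form. The anti-emetic dose count has no rule on indication or order type, and itching has a single treatment-based measure. With unblinded care, historical controls and no adjustment for practice or calendar time, either comparison can differ between groups with no difference in symptoms.

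Direction and size are unknown. The 12.5% shift and the rejection rates above rest wholly on assumed shares, counts and dispersion. Section 3.2 expects side effects to fall only as a hypothesis and does not make them a test of the primary conclusion. The primary outcome and the emesis count are unaffected. This is a worthwhile, inexpensive improvement to two secondary measures in a pilot, and it does not threaten the trial's main result.

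Section 15.1 says that the measures are repeated in an attachment, which was not available. The conclusion assumes that the attachment adds no counting rule.

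**What to change.** In 15.1, apply one abstraction rule to both cohorts:

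- Count the core anti-emetics on the list, showing scheduled and PRN doses separately. Do not restrict the count to PRN doses. That would drop scheduled treatment started because of nausea, and it would itself move with the mix of order types.
- Count Benadryl and lorazepam as nausea treatment only when the order indication is nausea or vomiting. Report doses with no stated indication separately, and include them in a sensitivity count.
- Under itching, count antihistamine doses ordered for pruritus beside naloxone days.

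In 15.3, state that the emesis count is the lead nausea outcome and that the anti-emetic count is supportive, and name the model for the latter.

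The cost is slightly more abstraction work in the medication record, which 15.1 already has abstractors open for opioids. Some historical orders may carry no indication, which is why the unspecified category is needed. Treatment, sample size and consent do not change.

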## MEDICAL PROTOCOL (HRP-590)

PROTOCOL TITLE: Magnesium sulfate as adjuvant analgesia and its effect on opiate use by post-operative transplant patients in the pediatric ICU.

VERSION DATE: 06/09/2022

### 4. Respiratory Variables

- # escalations required
- Peak respiratory requirement each day
- # Days intubated

### Other pain/comfort variables

1. FLACC, Pain Score (self-reported), comfort B scores - daily and total/day
2. PICU duration – post-operative day when transfer order placed (i.e. POD#7)
3. Intubation
  - # of days intubated – will track as earliest post-operative day extubated (i.e. POD#1)
  - # of re-intubations
4. Paravertebral Block – whether used (yes or no), # of times dose increased
5. Ketamine use – total mg/kg, mg/kg/d
6. Total doses and doses/day: Acetaminophen, Ketorolac, ibuprofen, celecoxib, gabapentin, amitriptyline
7. Dexmedetomidine – total mg/kg, mg/kg/day, peak dose
8. Midazolam - whether infusion required each day
9. PT involvement (# successful visits, POD# at initiation)
10. Feeding Advancement (day at initiation, day at goal feeds)

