## MEDICAL PROTOCOL (HRP-590)

PROTOCOL TITLE: Magnesium sulfate as adjuvant analgesia and its effect on opiate use by post-operative transplant patients in the pediatric ICU.

VERSION DATE: 06/09/2022

outcomes (total days on IV opioids, number of PCA demands and deliveries, number of infusion dose escalations, number of ileus events, days until first stool, emesis counts, number of days naloxone infusion required, PICU duration, number of days intubated, paravertebral block dose increases), categorical outcomes (ketamine use, presence of side effects), and continuous outcomes (FLACC, Pain Score). Longitudinal measurements of magnesium, other analgesics, ionized calcium, PTH, and creatinine levels will be analyzed using mixed effects models. Group summaries including means, standard deviations, and rates will be reported and group differences will be summarized as incidence rate ratios, odds ratios, or mean differences with 95% confidence intervals. Analyses will be conducted using the intent-to-treat principle; control group participants who underwent magnesium replacement (for hypomagnesemia or pre-designed post-transplant protocol) will be included in the control group, and experimental group participants with discontinuation of magnesium, if any, will be included in the experimental group. A two-sided 5% level result will be regarded as significant. Statistical analysis will be per statistician's updated STATISTICAL ANALYSIS SOFTWARE (also used in a previous pain study with TPIAT cohort).

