### ***Classification of an Adverse Event***

Mild: Events require minimal or no treatment and do not interfere with the participant's daily activities  
— Moderate: Events result in a low level of inconvenience or concern with the therapeutic measures. Moderate events may cause some interference with functioning. — — Severe: Events interrupt a participant's usual daily activity and may require systemic drug therapy or other treatment. Severe events are usually potentially life-threatening or incapacitating. Of note, the term "severe" does not necessarily equate to "serious".

Of note, we do not intend to report mild side effects which are known to frequently occur in TPIAT and Liver transplants. For example, we will not report individual episodes of nausea/emasis, post-operative pain, ventilator adjustments (unless an escalation to new mode of respiratory support), non-sustained hypertension/hypotension on routine vital checks, anticipated returns to OR (for example to close abdomen after initial surgery). Similarly, known/predicted intraoperative fluctuations in coagulopathy, bleeding, and vitals trends will not routinely be reported, unless not responding to expected interventions per OR team. All of the above will be reported if medical team experts (i.e. surgeon or anesthesiologist in OR, intensivist in PICU) believe these above symptoms are contributing to an atypical course or a worsening in patient's expected trajectory.

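### Days intubated is defined as the day of first extubation, so ventilated days after a re-intubation are left out of a named count outcome

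*Combined protocol and SAP*

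**What the plan says.** Intubation time appears in three places.

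- Section 15.1, opioid side effect variables, Respiratory Variables: the number of "Days intubated" is listed without a definition. The same list collects the number of "escalations required" and "Peak respiratory requirement each day".
- Section 15.1, Other pain/comfort variables, Intubation: the number of days intubated is listed again, now with a rule, namely that the study "will track as earliest post-operative day extubated". The next line collects the number "of re-intubations".
- Section 15.3: "number of days intubated" is among the count outcomes compared between groups with generalized linear models. Re-intubations, escalations and peak respiratory support are not named there. The nearest entry is a general categorical one for side effects.

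Section 13.1 lists "respiratory depression (secondary to muscle weakness") and increased sedation among the foreseeable risks of magnesium. Section 5.2 says that control charts are abstracted in the same way as those of the prospective cohort.

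**The concern.** The label and the analysis treat the variable as a duration, but the rule records the time of a first event. The two agree for a child extubated once and part company for a child who is re-intubated. By collecting a re-intubation count, the plan itself allows that intubation may restart.

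The error runs one way within a patient: recorded time can fall short of true ventilated time but cannot exceed it, and the shortfall falls only on children in whom extubation failed. Those children matter for a drug whose listed risks include weakness, respiratory depression and sedation. If re-intubated time differed between the groups, the reported comparison of ventilated days would be wrong by that difference. A report built on section 15.3 as written would give a reader no sign of it.

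**Working it through.** The plan states no figure for this outcome that could be reproduced. The power table in section 15.2 concerns opioid dose. The check therefore applies the written rule to example patients and then sizes the shortfall.

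**Inputs.** The recording rule comes from section 15.1 and the analysis from section 15.3. Group sizes are 30 treated and 60 controls (section 10.1). The documents give neither a re-intubation rate nor a duration, so both are assumed below.

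**Step 1: apply the rule to constructed patients.**

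| Course | Recorded | Total days intubated |
|---|---|---|
| Extubated once, POD1 | 1 | 1 |
| Extubated POD1, re-intubated POD3, extubated POD6 | 1 | 1 + (6 − 3) = 4 |
| First extubation delayed to POD4 | 4 | 4 |

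The first two children score the same although one was ventilated for three more days. The third is counted in full. The rule therefore misses time after re-intubation but does not miss delayed first extubation.

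**Step 2: mean shortfall among treated patients.** With k of 30 re-intubated for L days each, the shortfall is k × L / 30.

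- k = 1, L = 3: 3/30 = 0.10 day
- k = 3, L = 4: 12/30 = 0.40 day
- k = 3, L = 5: 15/30 = 0.50 day

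A wider assumption of 5% to 20% re-intubated for 2 to 5 days gives 0.05 × 2 = 0.10 to 0.20 × 5 = 1.00 day per patient.

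**Step 3: effect on the group comparison.** The recorded mean difference (treated minus control) departs from the true one by −(treated shortfall − control shortfall). With 4 days per re-intubation:

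- 3 of 30 treated, 6 of 60 controls: −(12/30 − 24/60) = −(0.40 − 0.40) = 0
- 3 of 30 treated, 0 of 60 controls: −(0.40 − 0) = −0.40 day, which flatters magnesium
- 0 of 30 treated, 6 of 60 controls: −(0 − 0.40) = +0.40 day, which counts against magnesium

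Undercounting within a patient is thus one-sided, but the bias in the mean difference can be zero or take either sign. Section 15.3 also allows incidence rate ratios. On that scale, an equal shortfall in both groups would move the ratio further from 1 whenever first-extubation times differ.

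**Step 4: can other planned variables supply the missing time?** The re-intubation count gives events, not days. Escalations are also a count. Daily peak support could probably identify ventilated days, but no such derivation is planned and section 15.3 does not name the variable.

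**The case against.** The strongest reply has four parts.

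- **Respiratory harm is well covered elsewhere.** The variable registers weakness or over-sedation that delays first extubation. The chart variables add re-intubations, escalations and daily peak support, in both groups. Section 18.2 records respiratory decline needing a higher level of support, and section 12.3 halts the study after one respiratory failure attributed to magnesium. All of this stands. A reader might infer that the data cannot show respiratory harm, and the documents do not support that. However, the provisions in sections 18.2 and 12.3 concern treated patients only and do not supply a comparison with the retrospective controls.
- **The undefined listing under Respiratory Variables could be read as a plain day count.** It could, and section 15.3 does not say which listing it analyses. But an undefined entry does not override the only rule given for the same quantity.
- **The outcomes named in section 15.3 may not be exhaustive.** This is fair. Several other section 15.1 items are also unnamed, so omission does not prove that re-intubations will go unanalysed. It does leave their analysis unstated.
- **Recording by post-operative day is an open convention, used also for PICU duration and magnesium days.** Day of first extubation is a legitimate measure under its own name. The objection is to using it as the number of days intubated.

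A reader might also infer that re-intubation is expected to be common, because section 18.2 mentions "anticipated returns to OR (for example to close abdomen after initial surgery"). That does not follow. A child kept intubated until closure is counted correctly, and no frequency of re-intubation is given anywhere.

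**Conclusion.** The point holds as a mismatch between an outcome's name and its recording rule. As written, section 15.3 would analyse the day of first extubation as though it were the number of days intubated, and any ventilated time after a re-intubation would be left out.

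The size rests on assumed inputs. With 1 to 3 of 30 treated children re-intubated for 3 to 5 days each, 0.10 to 0.50 day per treated child is uncounted. The mean difference is biased only as far as re-intubated time differs between groups, and the documents offer no evidence that it does.

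A reader might go further and quote a hidden rate ratio. For example, 0.40 day on top of an assumed control mean of 1.5 days gives 1.9/1.5 = 1.27. That figure needs an assumed control mean, an assumed treated rate and no re-intubations at all in 60 controls, so it is not evidence about this trial.

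This is a minor correction to one secondary outcome in a pilot. It does not touch the primary outcome or the sample size.

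**What to change.** - In section 15.1, give both listings one definition: total days intubated in the PICU, summed over the first intubation and every re-intubation, with one stated day-counting rule for both groups.
- Use that variable in section 15.3.
- Keep the post-operative day of first extubation as a separate, separately named variable.
- Name the re-intubation count among the outcomes in section 15.3.

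The cost is slightly more chart abstraction: the start and end of each intubation instead of the first extubation alone. The source is the medical record already being reviewed, abstracted in the same way for treated and control patients (section 5.2). No patient procedure is added.
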